An additional limitation is that the study may be underpowered to detect small effects (HRs <1.2) if the outcome is very rare (<0.5%).

U. Plans for dissemination and communication of study results

Results will be presented at conferences (e.g. ICPE, SER) and submitted for publication in peer-reviewed journals (e.g. Lancet Respir. Med, Pharmacoepidemiology and Drug Safety).

V. Data Storage and Security

The data will be stored on a secure data server, within the London School of Hygiene and Tropical Medicine network. Access will be restricted to named users with specific involvement in the project.

The analysis dataset including those variables (exposures, outcomes, covariates) justified in the protocol and used for the analysis as outlined in the protocol will be archived on an Electronic Health Records Research Group drive on the LSHTM school network.

Data will remain on the secure server for the duration of the project, or until the end of the data retention period stipulated by the data owners. After this time, all data will be destroyed following the CPRD guidelines using dedicated software.

Analysis code will be uploaded on GitHub.

W. Ethics approvals

The data used in this project are routinely collected and anonymised data from the Clinical Practice Research Datalink (CPRD). The CPRD Group has in place ethical approval from a National Research Ethics Service Committee (NRES) for all purely observational research using anonymised CPRD data; namely, studies which do not include patient involvement (including this study, see <https://www.cprd.com/content/guidance-completion-cprd-research-data-governance-rdg-application>).

The current project (which does not include patient involvement) does fall within the overall scope of existing CPRD approvals. However, all projects using CPRD data have to obtain additional approval from the CPRD Research Data Governance (RDG). CPRD RDG committees review protocols for feasibility, public health benefits/risks and information governance risks. A scientific proposal has been submitted to the CPRD RDG and approved by CPRD Research Data Governance (CPRD reference 22_001876).

Additionally, the project has been approved by London School of Hygiene and Tropical Medicine Ethics Committee (Project ID: 27896).

X. Expected timelines

Start of funding: 19/04/2021

Registration in EU PAS register: 11/07/2022

Start of data collection/extraction: 01/09/2022

Start of data management: 01/09/2022

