D. Aims, objectives, rationale

The aim of this study is to investigate the effects of ICS at different stages of the COVID-19 disease pathway (i.e., infection, hospitalisation, and death) among patients with asthma or COPD and apply methods of QBA to these effect estimates to account for potential biases arising in these estimates of association. The null hypothesis is that use of ICS has no effect on COVID-19-related outcomes.

Objectives

- A. To describe prescription patterns of ICS among patients with respiratory diseases before and during the COVID-19 pandemic.
- B. To investigate the association between prevalent ICS use and COVID-19 related outcomes among patients with respiratory diseases.
 - a. Estimate the association between prevalent ICS use and risk of having a positive SARS-CoV-2 test.
 - b. Estimate the association between prevalent ICS use and risk of hospitalization with COVID-19 among patients with a positive SARS-CoV-2 test.
 - c. Estimate the association between prevalent ICS use and risk of death among patients who were hospitalized with COVID-19.
- C. To develop approaches and apply methods of QBA to account for potential biases arising in these estimates of association.
 - a. Investigate impact of exposure misclassification (e.g., due to stockpiling of medication, patients not filling prescription or underascertainment of in-hospital medication use) on estimates from objective 2a, 2b, and 2c.
 - b. Quantify potential biases due to unmeasured or unknown confounders on estimates from objective 2a, 2b, and 2c.
 - c. Investigate impact of outcome misclassification (e.g., underascertainment of infections due to limited testing availability and non-random testing) on estimates from objective 2a.
 - d. Investigate impact of selection bias (e.g., non-random selection of individuals into a study) on estimates from objective 2b and 2c.

E. Outcomes

COVID-19 positive test result; hospitalisation with COVID-19; death with COVID-19, as defined in section N.

F. Study type

The overall study design is a historical cohort study.

G. Study design

Objective 1 will be a descriptive study with a population-level description of prescription patterns of ICS before and during the COVID-19 pandemic among patients with respiratory disease.

Objective 2 will be a hypothesis testing cohort study. The null hypothesis is that there is no association between ICS use and testing positive for COVID-19, hospitalisation for COVID-19 and death with COVID-19.

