Furthermore, 1,031,882 patients who received a prescription for ICS between 01st March 2019 and 29th February 2020 were identified. Of the patients with asthma, 485,192 had a prescription for ICS. Of the patients with COPD, 83,668 had a prescription for ICS.

		With ICS prescription 01/03/2019-29/02/2020
Asthma	755,632	485,192 (64.2%)
COPD	225,472	83,668 (37.1%)

K. Sample size considerations

Between 01st March 2020 and 31st August 2020, 295,134 positive SARS-CoV-2 tests were reported in England.³⁷ Based on a population of 56,550,000³⁸, that corresponds to 0.52% of the population testing positive for SARS-CoV-2. During that time period, 36,974 deaths with COVID-19 occurred in England, corresponding to 0.065% of the population.

Table 1. Sample size calculations for $\alpha = 0.05$ and 80% power, assuming 64% of the study population are prescribed ICS.

Outcome probability in controls	HR=1.1	HR=1.2	HR=1.3	HR=1.4	HR=1.5	HR=1.6	HR=1.7
0.05%	7,500,266	2,049,648	989,797	601,807	414,428	308,428	241,978
0.1%	3,750,133	1,024,824	494,899	300,904	207,214	154,214	120,989
0.2%	1,875,067	512,412	247,450	150,452	103,607	77,107	60,495
0.3%	1,250,045	341,608	164,967	100,302	69,072	51,405	40,330
0.4%	937,534	256,206	123,725	75,226	51,804	38,554	30,248
0.5%	750,027	204,965	98,980	60,181	41,443	30,843	24,198
0.6%	625,023	170,804	82,484	50,151	34,536	25,703	20,165
0.7%	535,734	146,404	70,700	42,987	29,602	22,031	17,285
0.8%	468,767	128,103	61,863	37,613	25,902	19,277	15,124
0.9%	416,682	113,870	54,989	33,434	23,024	17,135	13,444
1.0%	375,014	102,483	49,490	30,091	20,722	15,422	12,099

Assuming the probability of testing positive for SARS-CoV-2 among people with asthma or COPD is equal to or higher than the probability of testing positive among the general population, this study will likely be adequately powered to detect HRs of 1.1 or higher in the asthma population and 1.2 or higher in the COPD population for the outcome of testing positive. For the rarest outcome, death, the study would be powered to detect HRs higher than 1.4 in the asthma cohort and 1.7 in the COPD cohort.

L. Study population

Descriptive study

For the descriptive study, we will examine prescription patterns of ICS in two cohorts: patients with COPD and patients with asthma. Follow-up will be from 1st March 2019 until the end of wave 2 of COVID-19 in the UK (30th April 2021).

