For each cohort and each calendar month, the study population will consist of people who have a record of asthma or COPD. For the asthma cohorts, each monthly cohort will consist of those patients who, on the 15th of each month (the index date), had 1) their first asthma code on or before that date; and 2) did not have COPD on or before that date.³⁹ Correspondingly, for the COPD cohorts, each monthly cohort will consist of those patients who, on the 15th of each month, had 1) their first COPD code on or before that date; and 2) did not have asthma on or within 3 years before that date. To be included in a cohort, patients must have at least one year of follow-up in CPRD prior to the index date and have age and gender recorded in CPRD.

Comparative cohort studies

For the comparative cohort studies, the study population will consist of two separate, mutually exclusive disease cohorts, a COPD cohort and an asthma cohort, consisting of patients registered with GP practices meeting CPRD quality control standards. For each disease cohort (asthma and COPD), two cohorts will be created, one for the first wave of COVID-19 and one for the second, defined relative to a cohort entry date (1st March 2020 for wave 1, 1st September 2020 for wave 2), to make a total of four cohorts. To be included in a cohort, patients must have at least one year of follow-up in CPRD prior to the cohort entry date, be eligible for linkage to HES data, and have gender and age recorded in CPRD.

Asthma cohort⁴⁰

The asthma cohort will include all adults aged 18 and over with a recorded diagnosis of asthma defined as a record of asthma within 3 years prior to the cohort entry date. This method of identifying asthma has previously been validated in CPRD.⁴⁰ Code lists to identify asthma will be reviewed by a clinical expert before use.

Patients will be excluded if they have a record of COPD or any other chronic respiratory condition at any point before the cohort entry date, or a prescription of a LAMA but no ICS within 3 years before the cohort entry date, as this indicates possible COPD. Patients who received a prescription of nebulised medication within 1 year before the cohort entry date will also be excluded, as this indicates very severe asthma.

COPD cohort⁴¹

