before the previous one is estimated to have been completely used, we will assume stockpiling occurred and assign the maximum total days of exposure possible with the combined prescriptions. Patients who switch treatment groups will be considered exposed to the active comparator/ICS group from the date of the switch, and those who discontinue treatment or switch to a treatment not under study will be censored at discontinuation or switch.

Patients will be considered exposed from the date the prescription was issued, as ICS have been shown to exert anti-inflammatory effects within hours of administration.⁴³

Outcomes

- SARS-CoV-2 infection, defined as a recorded positive test for SARS-CoV-2 in the primary care record sourced from the Second Generation Surveillance System (SGSS).
- hospitalisation with COVID-19, defined as admission to hospital with an ICD-10 code for COVID-19, ascertained using HES data.
- death with COVID-19, defined as death with an ICD-10 code for COVID-19 listed as an underlying or contributing cause of death in the ONS death registry.

Covariates

- demographic and lifestyle variables at baseline: age, sex, body mass index (BMI), smoking status, ethnicity, socioeconomic status (Index of Multiple Deprivation, IMD)
- ever-present comorbidities at baseline: chronic kidney disease, hypertension, heart failure, other heart diseases, diabetes, cancer, immunosuppression
- time-updated covariates: influenza vaccination within one year before the cohort entry date, pneumococcal vaccination within 5 years before the cohort entry date, vaccination against COVID-19 (wave 2 only)
- calendar time, COVID-19 prevalence figures (ONS)
- asthma cohort only: number of recorded asthma exacerbations (emergency department visit, hospitalisation or prescription of an oral corticosteroid for asthma⁴⁴) within 1 year before the cohort entry date
- COPD cohort only: number of recorded COPD exacerbations (defined using a validated algorithm⁴⁵) within 1 year before the cohort entry date.

O. Data analysis

Descriptive study:

Population-level measures of ICS use that will be determined per calendar month are:

- Number and proportion of incident and prevalent users over the course of follow-up for each calendar month:
 - Prevalent ICS exposure will include people with an ICS prescription recorded on any day during that month.

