Exposure misclassification may arise due to low adherence to inhaled medication for respiratory diseases⁴⁷⁻⁴⁹, and due to stockpiling of medication⁴⁷ at the beginning of the pandemic (March and April 2020). The descriptive cohort study (objective 1) will investigate prescription patterns and the potential extent of stockpiling during the pandemic. To adjust for potential exposure misclassification, we will calculate proxy measures for adherence (proportion of days covered or medication possession ratio) in the year before the COVID-19 pandemic (March 2019 – February 2020) and use these, together with data from literature and input from clinicians, to estimate adherence during the pandemic. Additionally, we are looking to obtain questionnaire data on adherence during the pandemic from the Optimum Patient Care Research Database (OPCRD). If this data is not obtained, or is not suitable for these purposes, we will estimate exposure misclassification using data from literature and input from clinicians.

In objective 2a, the outcome of SARS-CoV-2 infection may be misclassified as testing was conducted in a non-random manner. Especially in the first wave of COVID-19, testing was very limited, and therefore not all infections will have been ascertained. It is plausible that the probability of getting tested for SARS-CoV-2 was not equal among people prescribed ICS and those not prescribed ICS, resulting in differential misclassification of SARS-CoV-2 infection. We will use test data from CPRD and data from the ONS infection survey to estimate how many SARS-CoV-2 infections may have been missed in the respective study populations. We will work together with clinicians to create plausible bounds for sensitivity and specificity of the outcome classification.

Selection Bias:

Analyses that are restricted to people who received a positive test for SARS-CoV-2 or were hospitalised with COVID-19 may be vulnerable to selection bias. Potential differential misclassification of SARS-CoV-2 infections in objective 2a would result in selection bias in objective 2b, as selection into the study

population is conditional on a positive test for SARS-CoV-2. In order to adjust for selection bias, the bias parameters necessary are the selection probabilities S for each combination of exposure E and outcome D :

- Probability of being selected into the study conditional on being exposed and experiencing the outcome ($P(S|D=1, E=1)$),

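### Objective 2b does not require the positive test to precede the COVID-19 admission, so its hazard ratio mixes progression to hospital with testing prompted by admission

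*Protocol*

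**What the plan says.** The aim in section D of the protocol is to "investigate the effects of ICS at different stages of the COVID-19 disease pathway (i.e., infection, hospitalisation, and death"), so each step of the pathway is to be examined in its own right. Objective 2b (item B.b in the list in section D) takes the second step: "Estimate the association between prevalent ICS use and risk of hospitalization with COVID-19 among patients with a positive SARS-CoV-2 test".

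The pieces that define this analysis are:

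- **Entry to the population (section N).** A positive test is "defined as a recorded positive test for SARS-CoV-2 in the primary care record sourced from the Second Generation Surveillance System (SGSS"). Neither the setting of the test nor its timing relative to admission is restricted.
- **Event (section N).** "hospitalisation with COVID-19, defined as admission to hospital with an ICD-10 code for COVID-19, ascertained using HES data". The test date plays no part.
- **Time zero (section L).** Four cohorts are created, "defined relative to a cohort entry date (1st March 2020 for wave 1, 1st September 2020 for wave 2"). No separate entry date is given for 2b.
- **Follow-up (sections L and O).** One exit rule serves all cohorts, and the Cox model uses time in study.

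Section P accepts that in wave 1 "testing was very limited, and therefore not all infections will have been ascertained". It says that differential ascertainment of infection would carry over into 2b as selection bias, and it plans to multiply the observed estimate by an odds ratio built from four selection probabilities. Section O adds an analysis that drops the conditioning on a positive test.

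**The concern.** Two different patients satisfy the 2b definitions. One tests positive in the community and is later admitted, which is progression. The other is admitted first and swabbed on the ward. The second belongs to the 2b population only because the outcome has happened, and is then counted as having it. Nothing in the protocol separates them.

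Where testing outside hospital is scarce, almost all admitted infections but few others enter the population. The outcome becomes common among those selected, and a hazard ratio estimated there is compressed. If the chance of a community test also differs between ICS users and comparators, the ratio can move away from 1 with no true effect.

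The population, event, time zero and time scale are all fixed in the protocol, so this is not a detail left open for a later analysis plan.

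**Working it through.** **1. The protocol's own figures.** Section K gives 295,134 positive tests in England in wave 1 and "36,974 deaths with COVID-19 occurred in England, corresponding to 0.065% of the population". With its population of 56,550,000, 295,134 / 56,550,000 = 0.522%, as stated. The ratio of deaths to reported positives is 36,974 / 295,134 = 12.5%. That is consistent with testing concentrated in severe cases, but it does not show where tests were taken, nor that the deaths occurred among those tested. It is not used below.

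**2. Inputs not in the documents (assumed).** Admission risk after infection r = 5% in comparators and 7.5% in ICS users. All admitted patients are tested. A fraction t of non-admitted infections is tested, equal in both arms, from 2% to 20%.

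**3. Formulas.** Admission risk among test-positives: p = r / (r + (1 − r)t). Constant-hazard HR: ln(1 − p₁) / ln(1 − p₀).

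Truth: risk ratio 1.5; HR = ln(0.925) / ln(0.95) = 1.52; odds ratio (OR) = (0.075/0.925) / (0.05/0.95) = 1.54.

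| t | p₀ | p₁ | Risk ratio | HR | OR |
|---|---|---|---|---|---|
| 2% | 0.725 | 0.802 | 1.11 | 1.26 | 1.54 |
| 5% | 0.513 | 0.619 | 1.21 | 1.34 | 1.54 |
| 10% | 0.345 | 0.448 | 1.30 | 1.40 | 1.54 |
| 20% | 0.208 | 0.288 | 1.38 | 1.46 | 1.54 |

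A simulated Cox model with entry on 1 March and t = 5% gave an HR of about 1.3, close to the closed form. With equal t and no true effect, p₁ = p₀ and the HR is 1.

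**4. The planned correction.** The selection OR that corrects the estimate is P(S|D=0,E=1) × P(S|D=1,E=0) / [P(S|D=1,E=1) × P(S|D=0,E=0)]. Here that is (t × 1) / (1 × t) = 1. It is exact for an OR, which was never distorted, but it returns the compressed HR unchanged.

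Using the same four probabilities on the cells does work. At t = 5%, per 10,000 infections in each arm, the observed cells are 500 admitted and 475 not (comparator), and 750 and 462.5 (ICS). Dividing each by its selection probability gives 500 and 9,500, and 750 and 9,250, so the risk ratio is 1.5 again.

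**5. Unequal testing under a true null.** Take r = 5% in both arms and t = 5% in comparators.

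- ICS t = 4%: p₁ = 0.05 / (0.05 + 0.95 × 0.04) = 0.568, so HR = 1.17. The correction factor 0.04/0.05 = 0.8 takes it to 0.93.
- ICS t = 6%: p₁ = 0.467, so HR = 0.88. The factor 1.2 takes it to 1.05.

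Multiplying an HR by a selection OR overshoots in both directions when the outcome is common.

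**6. Events left once the test must come first.** The section J counts times 0.522% give about 3,944 asthma and 1,177 COPD test-positives in wave 1. Assume 30% are first tested at admission, a 10% admission risk after a community positive in comparators, and a true ratio of 1.3. With 64.2% and 37.1% on ICS:

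- Asthma: 3,944 × 0.7 × 0.10 × (0.358 + 0.642 × 1.3) ≈ 329 events.
- COPD: 1,177 × 0.7 × 0.10 × (0.629 + 0.371 × 1.3) ≈ 92 events.

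Power from Φ(√(D·π(1−π))·ln 1.3 − 1.96), where D is the number of events and π the proportion on ICS, is 0.63 and 0.23. The section J counts precede the section L exclusions, so these figures are probably optimistic.

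**The case against.** The strongest reply is that selection through testing is what this study sets out to examine. Section C names it, objective C.d targets it for 2b, section P asks for all four selection probabilities, section O plans an unconditioned analysis, and section T lists collider bias as a limitation to be addressed. Much of this stands: the type of bias is declared and the inputs for a working correction are planned. What it does not cover is the order of test and admission. The correction as written is applied on the wrong scale for a common outcome, and the unconditioned analysis combines infection with progression and so answers a different question.

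Four stronger readings are tempting and are not supported:

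- **Progression is not measured at all.** Patients tested in the community before admission contribute true progression events, so the estimate is a mixture.
- **A real effect would be reported as none.** In the worked example the HR stays at 1.26 or above, and a true null stays null when testing is equal by arm.
- **The 12.5% proves that testing was hospital-driven.** The protocol says testing was limited and non-random; it does not say where it was done.
- **Attenuation is nearly complete.** Fixing the share of positives found at admission at 30% in both arms turns a true risk ratio of 1.3 into 1.03 to 1.10. But if admission prompts testing, that share must rise with admission risk: at t = 5% it is 0.51 for a 5% risk and 0.58 for 6.5%. The equal-share model does not describe this mechanism.

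It is also fair that this overlaps with the choice of time zero. An ordering rule alone would leave follow-up before the test free of events by definition, so the two need one joint fix.

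**Conclusion.** The point holds as a defect in the definition of 2b. Patients first tested at or after admission are events by construction, and the hazard ratio blends two processes that the aim wants kept apart. With equal testing by arm the effect is attenuation: a true HR of 1.52 appears as about 1.26 to 1.46, and the planned multiplication leaves it there. With unequal testing a true null can shift, for example to 1.17 or 0.88 for a one-point difference in community testing around 5%.

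These sizes rest on assumed admission risks, complete testing of admitted patients and the assumed range of community testing. The protocol gives none of these, so the actual size is unknown. The problem is likely to be greater in wave 1, given the limited testing that section P describes. It warrants a change before analysis, but it does not invalidate 2b.

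**What to change.** Amend section D (2b) and sections L, N and O as follows:

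1. For 2b, start follow-up at the date of the first positive test and count only COVID-19 admissions after that date. State which date is used (specimen or report) and whether exposure stays anchored to the wave date.
2. Exclude from the conditional 2b analysis patients whose first positive test is on or after the admission date, with an explicit rule for same-day tests.
3. Report the number excluded by exposure arm and wave, and keep these patients in the unconditioned analysis already planned.
4. In section P, apply the four selection probabilities to the cells, rather than multiplying an HR by the selection OR, when the outcome is common. Define selection as testing positive before admission.

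The work is mainly a comparison of test and admission dates, provided a usable test date comes with the primary care record. The real cost is fewer events and less precision, mainly in wave 1 (about 329 asthma and 92 COPD events in the illustration). The result then applies to patients tested before admission. It recovers the true ratio only if community testing is unrelated to later admission, so the selection-bias analysis is still needed.

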Objective 3 will be a methodological study to develop and apply methods of quantitative bias analysis to account for potential biases arising in the estimates of the effects of ICS on COVID-19 outcomes.

H. Data source

This project will use the Clinical Practice Research Datalink (CPRD) Aurum, a database containing routinely collected patient data from GPs in the UK. CPRD Aurum includes data on 41 million patients (March 2022), with over 13 million patients currently registered (20% of the UK population).³¹ These patients come from over 1,300 GP practices which use EMIS GP patient management software.³¹ CPRD records information on diagnoses, symptoms, demographics and lifestyle factors, prescriptions, referrals, vaccinations and tests^{31,32}, coded using SNOMED and Dictionary of Medicines and Devices (DM+D) codes. CPRD Aurum has been shown to be broadly representative of the English population in terms of age, gender, geographical spread and deprivation.³²

I. Linked data

Data from CPRD can be linked to other databases such as the Hospital Episode Statistics (HES) and the Office for National Statistics (ONS) death registry. Both HES and ONS death registry data are linked to CPRD by NHS Digital using the NHS number, gender, date of birth and postcode.^{32,33} HES holds information on all patient contacts at NHS hospitals in England, with diagnoses recorded using International Classification of Disease 10th revision (ICD-10) codes.^{33,34} ONS death registry data contains information on all deaths occurring in England and Wales, including a cause of death documented using ICD-10 codes.^{34,35}

HES Admitted Patient Care will be used to identify hospitalisation with COVID-19. ONS death registration data will be used to identify death with COVID-19. Additionally, the Index of Multiple Deprivation (IMD) will be used as a covariate to adjust for socioeconomic deprivation, which has been associated with COVID-19 outcomes.³⁶

J. Feasibility counts

A feasibility count based on CPRD Aurum June 2021 build identified 225,472 patients with a COPD code before 29th February 2020, and 755,632 patients with an asthma code between 1st March 2017 and 29th February 2020. These patients were registered in CPRD on 1st March 2020 and had at least one year of registration prior to that date.

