The COPD cohort will include all adults aged 35 and over with a recorded diagnosis of COPD at any point before the cohort entry date.⁴¹ This method of identifying COPD has previously been validated in CPRD.⁴¹ Code lists to identify COPD will be reviewed by a clinical expert before use. To be included, patients must also have a record of current or former smoking in CPRD.

As in the asthma cohort, patients who have a record of other chronic respiratory conditions at any point before the cohort entry date will be excluded. People who use a leukotriene receptor antagonist (LTRA) within 3 years of the cohort entry date will be excluded as this indicates asthma, as will people who are prescribed a LABA/LAMA and ICS within 3 months before the cohort entry date, as this indicates severe COPD.

Censoring

For all cohorts, cohort exit will be defined as the first of either occurrence of the outcome (for each analysis), death, disenrollment from GP practice, the last date of data availability, or the end of the COVID-19 wave (31st August 2020 for wave 1, 30th April 2021 for wave 2).

M. Comparator groups

The study will use an active comparator group including all people with recorded asthma within 3 years or COPD at any point before the cohort entry date (1st March 2020 or 1st September 2020, respectively) who received a prescription for inhaled medication for asthma or COPD, but no ICS prescription.

The comparator group for the asthma cohort will be people who were not prescribed medication containing ICS and were prescribed a non-ICS inhaled medication for asthma. For the COPD cohort, the comparator group will include people who were not prescribed a medication containing ICS and were prescribed a LABA/LAMA separately or in combination for COPD. Exposures and exposure durations in the comparator group will be calculated in the same way as in the ICS-exposed group.

N. Exposures, outcomes and covariates

Exposure

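### The detectable hazard ratios in section K rest on all patients with a diagnosis code, not on the smaller active-comparator cohorts analysed, so the stated power is unsupported and probably too favourable

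*Protocol*

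**What the plan says.** Section J counts "755,632 patients with an asthma code between 1st March 2017 and 29th February 2020" and 225,472 patients with a COPD code. The only other conditions stated are registration on 1 March 2020 and one year of registration before it. ICS use is counted over 12 months: 485,192 of the asthma patients (64.2%) and 83,668 of the COPD patients (37.1%).

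Table 1 in section K is for "80% power, assuming 64% of the study population are prescribed ICS". From it the text concludes that, for testing positive, the study is likely to be "adequately powered to detect HRs of 1.1 or higher in the asthma population and 1.2 or higher in the COPD population", provided the risk is at least that of the general population. It adds: "For the rarest outcome, death, the study would be powered to detect HRs higher than 1.4 in the asthma cohort"; for the COPD cohort the figure is 1.7.

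Sections L and M define a narrower population. Patients must be 18 or over (asthma) or 35 or over (COPD) and eligible for HES linkage. Other chronic respiratory disease is excluded, as are COPD patients prescribed a LABA/LAMA with ICS in the 3 months before entry. The asthma comparator is "people who were not prescribed medication containing ICS and were prescribed a non-ICS inhaled medication for asthma"; the COPD comparator is LABA/LAMA users without ICS.

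Objective 2c (item B.c in section D) concerns "risk of death among patients who were hospitalized with COVID-19". Section T says "the study may be underpowered to detect small effects (HRs <1.2) if the outcome is very rare (<0.5" per cent).

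**The concern.** The power statement is attached to a population that the design does not analyse. The 270,440 asthma patients (755,632 − 485,192) and 141,804 COPD patients (225,472 − 83,668) without ICS include anyone who received no inhaler at all, and those people cannot be comparators. The other criteria reduce both arms.

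This matters because the asthma figure has almost no reserve: Table 1 asks for 750,027 patients at HR 1.1 and a 0.5% risk, against 755,632 counted. A reader of section K could expect a null finding to speak against an HR of 1.1 or 1.2 when the analysed cohort may be too small for that. The death figure has a further mismatch, since it uses the whole cohort while objective 2c uses hospitalised patients only.

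**Working it through.** **Inputs (protocol).** Alpha 0.05 and power 80% (Table 1; the table reproduces as two-sided). ICS share a = 0.64 in Table 1. Wave 1 risks: positive test 295,134 / 56,550,000 = 0.522%; death 36,974 / 56,550,000 = 0.0654%. Patient counts from section J.

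**Formulas (Schoenfeld).**
- Events needed: d = (1.960 + 0.842)² / [a(1 − a) ln(HR)²]; patients needed: N = d / risk.
- Power = Φ(ln(HR) √(a(1 − a)d) − 1.960).
- Detectable HR = exp(2.802 / √(a(1 − a)d)).

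**Reproducing the plan.** All 77 cells of Table 1 reproduce to within one patient. At HR 1.1, d = 3,750 and 3,750 / 0.005 gives 750,027 after rounding up. At HR 1.2, d = 1,025 and N = 204,965. With the full counts at the exact risks and a = 0.64, power is 81.9% for asthma HR 1.1, 85.1% for COPD HR 1.2, 94.8% for asthma death HR 1.4 and 87.1% for COPD death HR 1.7. The stated HRs therefore do follow from the unrestricted counts.

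**Reserve: the proportional loss of patients before power falls below 80%.**

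| Statement | N needed | N counted | Reserve |
|---|---|---|---|
| Asthma, positive test, HR 1.1 | 718,555 | 755,632 | 4.9% |
| COPD, positive test, HR 1.2 | 196,364 | 225,472 | 13% |
| COPD, death, HR 1.7 | 185,046 | 225,472 | 18% |
| Asthma, death, HR 1.4 | 460,217 | 755,632 | 39% |

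**Loss of comparators.** The analysed numbers are not in the protocol, so the shares below are assumptions. All ICS users are kept, the risks are 0.522% and 0.0654%, and a is recomputed each time. For example, with half of the asthma non-users: N = 485,192 + 135,220 = 620,412, a = 0.782, d = 3,238.

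| Non-ICS patients who qualify | Asthma HR 1.1: power (detectable HR) | COPD HR 1.2: power (detectable HR) | Asthma death HR 1.4: power | COPD death HR 1.7: power |
|---|---|---|---|---|
| 90% | 79% (1.10) | – | 93% | – |
| 75% | 74% (1.11) | 81% (1.20) | 90% | 84% |
| 50% | 61% (1.13) | 73% (1.22) | 80% | 76% |
| 25% | 39% (1.17) | 55% (1.28) | 55% | 57% |

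Asthma HR 1.1 drops below 80% once about 7% of non-users fail to qualify; COPD HR 1.2 does so once about 31% fail. If half of both COPD arms remain (N = 112,736), power at HR 1.2 is 57% and the detectable HR is 1.27.

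**Death as conditioned in objective 2c.** The full counts yield about 755,632 × 0.000654 = 494 asthma deaths and 225,472 × 0.000654 = 147 COPD deaths. If between all and half of these occur among hospitalised patients (assumption), the detectable HR is 1.30 to 1.45 in asthma and 1.61 to 1.97 in COPD, before any loss from sections L and M.

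**Objective 2b**, for which section K gives no figure. The full counts yield about 3,944 asthma and 1,177 COPD test-positives. If 10 to 30% are hospitalised (assumption), the detectable HR is 1.34 down to 1.19 in asthma and 1.71 down to 1.36 in COPD.

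**Section T beside section K.** At 0.0654% and with the full counts, asthma HR 1.3 needs about 756,900 patients (755,632 counted) and COPD HR 1.6 about 235,900 (225,472 counted). For death, the lack of power therefore reaches well above HR 1.2.

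**The case against.** A reader might infer that the study does not have the power it states. The protocol does not support that. The analysed numbers are not given, and the positive-test sentence is hedged: it says likely, and assumes a risk at or above the general population's. Power depends on events, so a higher risk can make up for fewer patients. If half of the non-ICS asthma patients qualified, a risk of about 0.82% instead of 0.52% would restore 80% at HR 1.1. Table 1 also labels its risk as that in controls; read that way, the full counts give 84% power for asthma HR 1.1 and 88% for COPD HR 1.2, and with 90% of asthma non-users qualifying power is about 82%. The rates cover wave 1 only. All of this stands, and it limits the conclusion to unsupported and probably overstated.

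Three other stronger readings also fail:
- The restriction to test-positive or hospitalised patients does not affect the positive-test sentence, which concerns objective 2a. For 2c it lowers N but raises the risk, so only deaths outside the hospitalised group are lost. The unconditional death analysis is planned, though as a sensitivity or additional analysis (section O).
- The 3-month ICS window is not settled. It belongs to the time-fixed option in section N; the time-updated option looks back a year, as the feasibility count does.
- Section T does not contradict section K. It does not say that power is lacking only below HR 1.2, so it is incomplete rather than false.

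Finally, this is a historical cohort of existing records. Power decides no recruitment, and results will be read from confidence intervals. That makes the point less serious, but it does not make a power statement right for a population that is not analysed.

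**Conclusion.** The point holds in this form: section K's detectable HRs are derived from every coded patient, while sections L and M analyse a subset of unstated size. The statement is least secure for asthma HR 1.1, where the reserve is 4.9% at 0.522% (0.7% at the 0.5% row of Table 1) and the requirement of another inhaler alone could exceed it. COPD HR 1.2 and COPD death HR 1.7 have moderate reserve. Asthma death HR 1.4 is robust to considerable loss and should not be called wrong. The death figures do not describe objective 2c. Using 64% rather than 37.1% exposed for COPD is immaterial, since a(1 − a) is 0.230 against 0.233.

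The sizes rest on the protocol's wave 1 general-population risks, read as overall risks, and on assumed shares of patients retained. The mismatch of populations rests on no assumption.

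**What to change.** 1. Recount patients by arm after all section L and M criteria, under whichever section N exposure definition is chosen.
2. Replace the power sentences in section K with minimum detectable HRs based on expected event counts and the actual ICS share in each disease cohort: for 2a, for 2b among test-positive patients, and for 2c among hospitalised patients. If the present death figures are kept, label them as belonging to the unconditional analysis.
3. Amend section T so that its limitation covers death at the HRs that section K itself reports.

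The cost is one feasibility query and rewording of two sections. The stated HRs will probably look less favourable. No more patients are needed, and the design and the analysis model do not change.
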